12.4 SAMPLE SIZE CALCULATION

Sample size protocol SOPH155-0415/IV

According to the objectives of the study to evaluate the Zebesten ® effect in subjects with primary pterygium, the variables of primary outcome stipulated in the design were:

- Conjunctival hyperemia
- TRL

Both variables are considered, using similar literature, to perform the calculation of the sample size to meet with the study objectives.

Conjunctival hyperemia

The sample size was calculated according to the formula for the continuous quantitative variables:

$$n = 2 \frac{(Z_{\alpha/2} - Z_{\beta})(\delta)}{d^2}$$

With a statistical trust of 95% that corresponds to the type I error, and is the same as 1.96, with a potency of 80% that corresponds to the type II error, and equals to 0.84. It is considered as a standard deviation for the increase of 0.4 degrees of severity1 in the scale of conjunctival hyperemia after a pterygium surgery, with an expected difference of at least 2.9 degrees of severity.

Based on the previous the result was 69 cases (eyes) per group, which was incremented 20% by consideration of the losses (14 subjects), with **a total of 83 cases per group**, with a total population of study of **166 eyes to treat**.⁸

Tear film breakup time

The sample size was calculated according to the formula for continuous quantitative variables:

$$n = 2 \frac{(Z \propto -Z_1 - \beta)(\delta)}{d^2}$$

With a statistical trust of 95% that corresponds to the type I error, and is the same as 1.96, with a potency of 80% that corresponds to the type II error, and equals to 0.84. It's considered as a standard deviation for the increase of 1.47 seconds 2 in the tear film breakup time posterior to 60 days of ciclosporin application A, with an expected difference of at least 10.2 seconds.

Based on the previous the result was of 120 cases per group, which was incremented 20% per consideration to the losses (24 cases), with a total of **144 cases per group**, with a total population of study of **288 eyes to treat**.

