13. STUDY VARIABLES

Independent variables

- Pharmacological intervention
 - Zebesten® + Sodium hyaluronate 4 mg/ml
 - Placebo (vehicle + Sodium hyaluronate 4 mg/ml)

Dependent variable

- Primary outcome variable
 - Conjunctival hyperemia
 - Tear film breakup time
 - Adverse events

- **Secondary outcome variable**

- burning
- Foreign body sensation
- Photophobia
- Questionnaire score OSDI
- Fluorescein stain
- Visual capacity
- Intraocular pressure

Intervening variables

- Work activity with sun exposure without ocular protection.
- Areas with air conditioner.
- Use of ocular devices that modify the lubrication.

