13.2 Security evaluation

The security variables of the use of Zebesten ® will be evaluated in the appointed visits in the chronogram, by means of the following parameters.

1. Tear film breakup time
2. Visual capacity
3. Intraocular pressure
4. Epithelial defects
5. Adverse events.

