13.3 Efficacy assessment

The efficacy variables of Zebesten® use will be evaluated in the appointed visits in the chronogram, by means of the following parameters:

1. Conjunctival hyperemia
2. OSDI score

Table of scales and variables measurement method

Variable	Unit	Symbol	Type	Measurement method	Normal value
Age	Years	--	Continuous	Calculated as of the date of birth	NA
Gender	Female Male	F/M	Nominal	Direct questioning	NA
Pterygium	Grade 0 Grade I Grade II Grade III Grade IV	--	Ordinal	Direct observation	Grade 0
Adverse events	Number of cases	N	Discreet	Counting	NA
Intraocular pressure	Mercury millimeters	MmHg	Continuous	Goldman applanation tonometry	11-21
Visual capacity	Fraction	Snellen	Nominal	Card	
Tear film breakup time	Seconds	s	Continuous	Direct counting	> 10
OSDI questionnaire	Points	--	Discreet	Questionnaire	
epithelial defects	Grade I Grade II Grade III Grade IV Grade V	--	Discreet	Direct observation with fluorescent staining and lissamine green	Oxford scale

Signs and ophthalmologic symptoms					
conjunctival hyperemia	Very mild Mild Moderate Severe	--	Ordinal	Direct observation. Efron classification.	Normal
burning	Present absent	--	Nominal	Direct questioning	Absent
Foreign body sensation	Present Absent	--	Nominal	Direct questioning	Absent
Photophobia	Present Absent	--	Nominal	Direct questioning	Absent
Prior segment	Normal Abnormal	--	Nominal	Direct observation	Normal

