14. PROPOSED STATISTICAL ANALYSIS

The statistical analysis will be performed by a researcher blinded to the intervention groups.

The continuous quantitative variables will be expressed and presented via measures of central tendencies and of dispersion (media, standard deviation and ranges).

The nominal qualitative variables and ordinals will be presented via frequencies and proportions.

The Kolmogorov-Smirnov test will be performed in order to know the normal distribution or not of the obtained results in each study group. Also, the Levene test will be performed in order to know if the variables are the same or different.

Assuming a normal distribution of the data, the intra-group differences will be determined via the t test for paired samples, in the case of the quantitative variables. For the quantitative variables the χ^2 test (chi squared) will be used and in case that the expected frequencies are less than 5 the exact Fisher test will be used.

The differences among the groups will be analyzed via the t test in case of quantitative variables. For the quantitative variables tables of contingency 2x2 will be made and the differences will be calculated via χ^2 (chi squared) with Yates correction in case that the expected frequencies are less than 5 the exact Fisher test will be used).

The level of significance will be alpha of 0.05 or less.

A final statistical analysis will be included to all the subjects that complete 3 visits in the chronogram of activities.

15. Results report

The results obtained during the development of the investigation's protocol will be the responsibility of the sponsor, who is under obligation of reporting them to the pertinent authorities. Plus each one of the participating researchers will receive a results report.

The objective is to achieve the publication of the study on an international magazine with the objective of disseminate the scientific knowledge obtained.

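### Section 14 applies an unsplit 0.05 and names no primary visit, success rule or multiplicity rule; if any one significant result counts, the false-positive rate is about 10% to 23.5%, depending on the outcomes and visits counted.

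*Combined protocol and SAP*

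**What the plan says.** **Outcomes.** Under "Primary outcome variable", Section 13 lists conjunctival hyperemia, tear film breakup time and adverse events, as does the Section 6 summary. Section 12.4 introduces its list with "the variables of primary outcome stipulated in the design were" and then names only hyperemia and breakup time.

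**Roles.** Section 13.2 (safety) opens its list with "1. Tear film breakup time" and also includes adverse events. Section 13.3 (efficacy) opens with "1. Conjunctival hyperemia" and adds only the OSDI score, which is secondary in Sections 6 and 13. Specific purpose 1 (5.1.1) is efficacy on hyperemia. Specific objective 2 (5.1.2) places breakup time under safety.

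**Visits.** The Section 9 schedule has hyperemia (within biomicroscopy) and breakup time at baseline and on Days 7, 15 and 21. Section 13.3 does not rank the visits: "The efficacy variables of Zebesten® use will be evaluated in the appointed visits in the chronogram".

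**Alpha.** Section 14 says "The level of significance will be alpha of 0.05 or less". Section 12.4 sizes each of its two outcomes with the same unsplit value: "With a statistical trust of 95% that corresponds to the type I error, and is the same as 1.96".

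Section 14 contains no primary visit, testing order, adjustment or statement of how many primary outcomes must succeed. Its reference to completing three visits defines who is analysed, not when the outcome is judged.

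**The concern.** A 5% error rate for the main conclusion requires that the deciding test be fixed in advance, or that several tests share the 5% by rule. Here there are at least two candidate outcomes and three candidate visits, and nothing written prevents success being claimed on whichever combination reaches significance.

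The lists also differ: three primary outcomes in Sections 6 and 13, two in Section 12.4. Someone writing the report could therefore defend more than one version of the primary analysis after seeing the data. What is at stake is whether a positive result carries the 5% error rate that the plan implies.

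**Working it through.** **The plan's own figures.** The plan states no family-wise error rate, so there is none to reproduce. What Section 12.4 shows is that alpha was not divided at the design stage: z = 1.96 (two-sided 0.05) is used for hyperemia (69 per group, 83 with losses, 166 eyes) and again for breakup time (120, 144, 288 eyes). Those sizes do not follow from their printed inputs. For hyperemia, 2 × (1.96 + 0.84)² × 0.4² / 2.9² = 0.30, which means 1 per group. That is a separate matter and does not affect the error rates below.

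**Inputs**
- Per-test level: 0.05, two-sided (Sections 14 and 12.4).
- Outcomes counted: hyperemia and breakup time (Sections 6, 12.4 and 13).
- Visits: Days 7, 15 and 21 (Section 9).
- Correlations: not given in the documents. Assumed 0.5 to 0.7 between visits and 0 to 0.3 between outcomes; wider range 0 to 0.9 and 0 to 0.7.
- Success rule: not given. Assumed that any one significant between-group result counts.

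**Independent tests.** The chance of at least one false positive in k tests is 1 − 0.95^k.
- k = 2: 1 − 0.95² = 9.75%
- k = 3: 1 − 0.95³ = 14.3%
- k = 6: 1 − 0.95⁶ = 26.5%

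**Correlated tests.** Test statistics are taken as jointly normal with no treatment effect on any outcome. The correlation between different outcomes at different visits is the product of the two correlations.

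| Tests counted | Main assumptions | Wider range |
|---|---|---|
| Hyperemia, three visits | 10.9% (visit correlation 0.7) to 12.5% (0.5) | 8.4% to 14.3% |
| Hyperemia and breakup time, one visit | 9.5% (outcome correlation 0.3) to 9.75% (0) | 8.4% to 9.75% |
| Hyperemia and breakup time, three visits | 20.1% (outcome 0.3, visit 0.7) to 23.5% (outcome 0, visit 0.5) | 13.7% to 26.5% |

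The top of the main range in the last row can be checked by hand. With a visit correlation of 0.5, one outcome over three visits gives 12.54%. Two independent outcomes then give 1 − (1 − 0.1254)² = 23.5%.

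**With the fix.** One outcome at one visit at 0.05 gives 5.0%. A fixed sequence, with breakup time tested only if hyperemia is significant, also holds 5%, because a first false positive can arise only at a single 0.05 step.

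**The case against.** **The protocol already implies an order.** Section 5.1.1 makes hyperemia the only specific efficacy target, Section 13.3 agrees, and the 166 eyes adopted in Section 7.2 equal the hyperemia figure. This stands in part. It makes the two-outcome figures the less certain case and leaves repeated visits as the main source of inflation. But an implied order is not an alpha rule, and it says nothing about which visit decides. Hyperemia alone with a free choice of visit still gives about 11% to 12.5%.

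**Inflation arises only if any one success is enough.** This is correct. If both outcomes had to succeed at one fixed visit, the error rate would not exceed 5%. The documents state neither rule, so the inflation is conditional. An all-must-succeed rule would also meet the protocol's own figure of 288 eyes for breakup time against the 166 planned.

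**The percentages look more exact than they are.** This also stands. The correlations are assumed, and every test is taken to have exactly 5% size. Section 13.3 classes hyperemia as ordinal, the Yates and Fisher tests in Section 14 are conservative, and counting both eyes of one subject as separate cases (7.2) works in the opposite direction.

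**Two stronger readings do not hold.** A reader might multiply three outcomes by three visits and report up to 1 − 0.95⁹ = 37%. The documents do not support that. Section 14 assigns no test to adverse events, Section 13.2 treats them as safety, the schedule also collects them at the Day 36 call, and a difference in them is not an efficacy success. A reader might also infer that the protocol contradicts itself by calling breakup time both primary and a safety variable. The general purpose covers efficacy and safety, so an outcome can be both. The real mismatch is the number of primary outcomes: two in Section 12.4, three in Sections 6 and 13.

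**Conclusion.** The concern holds in conditional form. As written, the plan does not secure a 5% error rate for its main conclusion, because it fixes neither the deciding outcome, nor the visit, nor how several results combine. If any one significant between-group result counts, the error is about twice the nominal level for hyperemia with a free choice of visit, or for two outcomes at one visit. It is four to nearly five times nominal for two outcomes over three visits.

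That the rule is missing can be read directly from Section 14 and needs no assumption. The size of the inflation rests on the any-success reading, the assumed correlations and exact 5% tests, so it is indicative. The documents do not show that the sponsor intends to claim success on any single result, only that nothing rules it out.

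**What to change.** - In Section 14, name the between-group comparison of conjunctival hyperemia at the final visit (Day 21) as the single primary efficacy test at two-sided 0.05, and name the test to be used. This follows specific purpose 1, the hyperemia-based 166 eyes, and the end of the 20-day treatment period.
- Describe the Day 7 and Day 15 comparisons as supportive.
- Report breakup time and adverse events as safety outcomes with 95% confidence intervals, in line with Section 13.2 (and 5.1.2 for breakup time). If a breakup-time claim is wanted, test it second in a fixed sequence, only if hyperemia is significant.
- Amend Sections 6, 12.4, 13 and 14 so that they give one list of primary outcomes. Section 12.4 must be included, because it names breakup time as primary and computes 288 eyes for it.

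The cost is wording in four sections, before unblinding, with no extra subjects. The downside is that breakup time can no longer support a claim on its own.

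Other rules would also control the error, such as 0.025 for each of two outcomes at one fixed visit (1 − 0.975² = 4.94% if independent) or requiring both to succeed. Either would keep breakup time primary, so the gap between 166 and 288 eyes would have to be resolved.

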History of autoimmune diseases that potentially can present ocular manifestations, like: rheumatoid arthritis, juvenile rheumatoid arthritis, Sjögren syndrome, seronegative spondyloarthropathies, Systemic lupus erythematosus, multiple sclerosis, arthritis of giant cells, Graves' disease, among others.

Infectious diseases

Ophthalmologic diseases that can potentially require treatment in the following 3 months.

Ocular surgical procedures (in the last 3 months)

Diseases in the previous segment that require treatment or endanger the visual prognosis (posterior uveitis, diabetic retinopathy, macular degeneration, etc.)

History of penetrating corneal transplantation.

History of scarring inflammatory diseases such as Steven-Johnson syndrome, pemphigus etc.

History of ocular allergic reaction and/or adnexa.

12.2.3 Elimination criteria of the subject included in the study:

1. Corneal damage clinically perceptible or evidenced in the staining of the surface (lissamine green and fluorescence) for example:

(a) Corneal de-epithelisation grade V (according to the Oxford scale)

(b) Corneal Melting.

(c) Corneal Dellen.

2. Added ocular surface diseases that require a treatment different to Zebesten ® or added treatments that are indicated for the new diagnostic.

3 Opacities in ocular transparent mediums (cornea, clear, vitreous body) that prevents the assessment of the anterior chamber or the following segment.

4. The subject's own decision.

5. Unable to keep the follow-up appointments.

6. Added not authorized treatment or self-medicated

7. Herbal treatments that affect the course of the disease or that produce other complications not related to the disease.

8. Systematic diseases that require immunomodulatory treatment or biologics that affect each line of the inflammatory cascade.

9. Retinal diseases secondary to chronic-degenerative diseases that require treatment to preserve the function and/or anatomy.

10. Inflammatory retinal diseases

11. Installation of uveitic picture in any ocular uveal level.

12. Uveitic picture that mean an ophthalmologic emergency that requires immediate treatment.

13. Ocular diseases that require surgical treatment.

14. Ocular diseases that require intravitreal injections.

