16.3 Subject discontinuation

The following are the reasons why a subject may leave the study prematurely:

Subject's decision. The subject that desires to leave the study for any reason is allowed to do so at any moment, but they must inform the researcher. In all cases, the researcher must try to establish contact with the subject as soon as possible for a final evaluation with the purpose of:

Documenting the subject's decision in clinical notes, obtaining the motive/s of the departure and writing them down in the exit format of the CRF, evaluate the clinical state of the subject, take timely therapeutic measures if required: handling of an adverse event or concomitant illness.

Researcher's decision. Especially if adverse events occur and the researcher considers that this can risk the subject's health, the indications in the adverse events section must be followed, or if an important disease occurs that needs medical prescription incompatible with the objective of the study. It will be reported in the clinical notes and a reporting format of the serious adverse events will be filled and the Ethics committee will be informed, clinical monitor and pharmacovigilance of Laboratorios Sophia.

An erroneous inclusion according to the protocol. The decision on whether the subject will remain in the study will be made conjunctly by the researcher and the sponsor.

Other motives (insufficient response, need of another treatment)

In all the cases, the available data will be kept for the security analysis (intention-to-treat population)

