16.5 Adherence to the treatment

Compliance of the administration of the study drugs by the subjects will be evaluated at the facilities of Laboratorios Sophia once the dropper bottle of each subject are returned by the researcher. Each bottle will be weighed in an analytical balance and the difference with respect to the initial weight of the bottle; all values above 70% will be considered as adequate adherence to the treatment with respect to the posology described in the present protocol for Zebesten® and the buyer. It will also be evaluated in the research center by the researching physician

In the event that the adherence to the study drug is under 70 %, it will be considered that the results obtained from the participant are analyzed by intention to treat, see the section for the statistical analysis.

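### The final analysis is based on subjects who complete an unspecified three visits, a condition arising after randomisation, and the two mentions of intention to treat elsewhere are never turned into an efficacy set or a missing-data rule

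*Combined protocol and SAP*

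**What the plan says.** Section 14 (Proposed statistical analysis) states the population once: "A final statistical analysis will be included to all the subjects that complete 3 visits in the chronogram of activities". It names no other set and says nothing about missing visits. It does say that the analyst is blinded to group, and section 7.3 keeps the blind during data analysis.

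The schedule in section 9 and the visit lists in sections 11.1 to 11.3 give four on-site visits: baseline, Day 7, Day 15 and Day 21. A telephone call follows at Day 36. Study treatment is handed over at baseline.

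Subjects can leave after inclusion in two ways:
- Section 12.2.3, "Elimination criteria of the subject included in the study", begins with "Corneal damage clinically perceptible or evidenced in the staining of the surface". It also lists unauthorised added treatment and inability to keep appointments.
- Section 16.3 adds the researcher's decision ("Especially if adverse events occur") and "Other motives (insufficient response, need of another treatment".

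Intention to treat appears twice, both times outside section 14. Section 16.3 says of leavers: "In all the cases, the available data will be kept for the security analysis (intention-to-treat population". Section 16.5, on adherence below 70%, says: "it will be considered that the results obtained from the participant are analyzed by intention to treat, see the section for the statistical analysis".

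**The concern.** A comparison restricted to subjects who reach a certain number of visits is not the comparison that was randomised. Some of the listed exits can plausibly depend on treatment. Corneal damage could fall more on the active arm: section 4 names corneal abrasion and corneal melting as adverse events of chronic topical use of this drug class, while adding that three weeks of bromfenac appears safe. Insufficient response or need of another treatment could fall more on the vehicle arm. Losing vehicle subjects who do badly would understate the drug effect; losing active subjects who do badly would overstate it.

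The rule is also open to more than one reading, so two analysts working from the same document could build different data sets. A reader sent by section 16.5 to section 14 for an intention-to-treat rule finds none.

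**Working it through.** **Step 1. What three visits can mean.** Every treated subject has the baseline visit, so attendance varies over Days 7, 15 and 21. That gives 2 × 2 × 2 = 8 patterns (1 = attended, in the order Day 7, Day 15, Day 21).

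| Reading | Patterns kept |
|---|---|
| A: baseline, Day 7 and Day 15 | 110, 111 |
| B: the three post-baseline visits | 111 |
| C: any three of the four | 110, 101, 011, 111 |

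A subject who misses only Day 7 or only Day 15 but attends Day 21 is kept under C and dropped under A and B. A subject with a single post-baseline visit, even Day 21 (001), is dropped under all three. Readings A and C admit subjects with no Day 21 data (110). These counts show ambiguity, not size: the patterns are not equally likely, and full attendance is kept under every reading.

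**Step 2. The three sections side by side.**

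| Section | Who it concerns | What it supplies |
|---|---|---|
| 14 | Subjects completing three visits | The final analysis; no intention-to-treat set, no missing-data rule |
| 16.3 | Subjects who leave early | Data kept for the security analysis, labelled intention to treat |
| 16.5 | Adherence under 70% | Intention to treat, by reference to section 14 |

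Section 16.5 does not restore a subject with fewer than three visits. Section 13.3 lists hyperemia and OSDI as the efficacy variables, and nothing clearly keeps leavers in for them. Section 13.2 lists breakup time and adverse events as security variables, so section 16.3 may cover them. Section 13 also makes both primary outcomes, so it is unclear which section sets their population.

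**Step 3. The plan's loss allowance.** Section 12.4 takes 69 eyes per group for hyperemia and adds 20%: 69 × 0.20 = 13.8, rounded to 14; 69 + 14 = 83 per group; 2 × 83 = 166. The allowance is therefore 14/83 = 16.9% of those enrolled. Section 12.4 does not say that a loss means failing the three-visit rule. How the 69 was obtained is a separate question on which this point does not depend.

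**Step 4. Assumed illustration of bias.** From the plan: 83 eyes per group, 14 lost, alpha 0.05. Assumed: the gap d, in SD, by which leavers do worse than completers in the same arm; eyes independent; no true effect.

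- Bias: b = f1·d1 − f2·d2, where f is the fraction lost.
- SE = √[DE × (1/n1 + 1/n2)], with n the eyes remaining and DE a design effect.
- Two-sided rejection rate = 1 − Φ(1.96 − b/SE) + Φ(−1.96 − b/SE).

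With 14/83 lost in each arm, n = 69 and 69, and SE = √(2/69) = 0.170.

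| d, one arm / other arm | DE | b (SD) | SE | b/SE | Rejection rate |
|---|---|---|---|---|---|
| equal in both | 1 | 0 | 0.170 | 0 | 5.0% |
| 0.5 / 0 | 1 | 0.084 | 0.170 | 0.495 | 7.9% |
| 1.0 / 0 (extreme) | 1 | 0.169 | 0.170 | 0.991 | 16.8% |
| 1.0 / 0 (extreme) | 1.5 (assumed) | 0.169 | 0.209 | 0.809 | 12.8% |

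The last row allows for section 7.2, under which both eyes of a subject can count as cases. If losses were only 5% per arm, n = 78.85, SE = 0.159, and even d = 1.0 against 0 gives b = 0.05 SD and a rate of about 6%.

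**The case against.** **Blinding.** The analyst is blinded, which limits choosing the population by its treatment result. That stands. It does not remove bias from unequal losses, and it does not tell the analyst which visits to require.

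**No intention-to-treat efficacy analysis was intended.** A reader might infer this, but the documents do not go so far. Section 14 does not exclude other analyses. Section 16.3 does not say that leavers' data serve security alone. Section 16.5 applies intention to treat to a participant's results without restricting it to safety. What the documents support is that intention to treat is invoked and never defined for efficacy.

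**Leavers' data are discarded.** A reader might also infer this from sections 12.2.3 and 16.3, which take subjects out of the study. Neither says that collected data are deleted. Under reading C, someone eliminated at Day 15 after attending every visit stays in. Exclusion comes from section 14, and it reaches those who leave before meeting its visit count.

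**Losses may be few.** Treatment lasts 20 days, and actual losses are unknown. This is fair, and the 5% case above shows how little may then be at stake. The plan's own allowance, however, is 14 of 83 per group.

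**Conclusion.** The concern holds as a defect in the analysis rule. The final analysis rests on an ambiguous condition that arises after randomisation and that treatment can affect. Sections 14, 16.3 and 16.5 are unreconciled, and no missing-data rule exists. The gap is clearest for hyperemia and OSDI; for breakup time and adverse events the population is unclear.

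A reader might go further and infer that the result will be biased, or biased in favour of the drug. The documents do not support that: they give no losses by arm and no outcomes for leavers, and equal, similar losses produce no bias. False-positive rates of about 8% (0.5 SD gap in one arm only) and about 17%, or 13% with the design effect (1.0 SD, extreme), rest on the assumed gaps, on 14 of 83 lost per arm and, apart from the 13% figure, on independent eyes. The case for change rests on the wording of the rule, not on these rates.

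**What to change.** - Make the primary efficacy set all randomised subjects, analysed as randomised, using all available post-baseline data.
- State a missing-data method (multiple imputation is one option), with a sensitivity analysis over a range of assumed outcomes for subjects without data.
- Keep two sensitivity sets: completers, defined by named visits, and subjects with adherence above 70%.
- State the population for breakup time and for adverse events.
- Report losses by arm and reason.
- Align sections 14, 16.3 and 16.5.

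The choice of primary time point is a separate matter.

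The cost is wording and modest analysis work, with no new visits. The estimate may move either way from the completer result. Leavers may contribute little follow-up, because section 16.3 says only that "the researcher must try to establish contact with the subject as soon as possible for a final evaluation"; this is why the sensitivity analysis is needed. The sets should be fixed before the data are unblinded.
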